After 15 subjects in Arm 3 have completed Visit 4, an interim analysis (interim analysis 3) will be performed to estimate the distribution of treatment effects on TUV and to optimize the TUV metric based on the interim data from all three Arms.

Efficacy Assessments:

Primary Endpoint(s)

ARMS 1-2

- The camera-specific precision of TUV_{joint} and TUV_{global} in HCs and subjects with active RA, which is defined as the Root Mean Square Difference (RMSD) between the consecutive 15-minute planar images.
- The stability of the mean/variance relationship, which is assessed by comparing the Coefficient of Variation (CV) of TUV_{joint} and TUV_{global} in HCs and subjects with active RA.

ARM 2

- The longitudinal (8-day) precision of TUV_{joint} and TUV_{global} in subjects with active RA, which is defined as the RMSD of images at the same time point.

ARM 3

- The correlation of $\Delta TUV_{global[5w]}$ and response to new anti-TNF α bDMARD therapy defined by the change from baseline (CFB) of CDAI to 12 ± 1 weeks and 24 ± 1 weeks ($\Delta CDAI_{12w}$ and $\Delta CDAI_{24w}$, respectively). The correlation of $\Delta TUV_{global[5w]}$ and response to new anti-TNF α bDMARD therapy from baseline

to 12 ± 1 weeks and 24 ± 1 weeks defined by ACR Response Criteria (ACR_{12w} and ACR_{24w}, respectively).

Secondary Endpoint(s)

ARMs 1-2

- The temporal stability of the 150 mcg tilmanocept mass dose/10 mCi radiolabeling dose

ARM 1

- The normal ranges of TUV_{joint} in HC subjects, which is defined as the 5 and 95 percentiles of:
 - TUV_{joint} of bilateral joints (i.e., bilateral wrists, metacarpophalangeal joint [MCPs], proximal interphalangeal [PIPs], knees, elbows, shoulders)

ARM 2

- The qualitative evaluations of SPECT/CT in detecting localization within synovial spaces of the bilateral hands and wrists

ARM 3

- The correlation of the TUV_{global[0week]} and response to new anti-TNF α bDMARD therapy defined by the change from baseline (CFB) of CDAI to 12 ± 1 weeks and 24 ± 1 weeks (Δ CDAI_{12w} and Δ CDAI_{24w}, respectively) and by ACR Response Criteria (ACR_{12w} and ACR_{24w}, respectively).
- The correlation of Δ TUV_{global[12w]} and Δ TUV_{global[24w]} and response to new anti-TNF α bDMARD therapy defined by the change from baseline (CFB) of CDAI to 12 ± 1 weeks and 24 ± 1 weeks (Δ CDAI_{12w} and Δ CDAI_{24w}, respectively) and by ACR Response Criteria (ACR_{12w} and ACR_{24w}, respectively).

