- The correlation of Δ TUV_{global[5w]} and constituent parameters of Δ CDAI_{12/24w} and ACR_{12/24w} including:
 1. Tender Joint Count (TJC)
 2. Swollen Joint Count (SJC)
 3. Patient assessment of global disease activity
 4. Rheumatologist assessment of global disease activity
 5. Patient assessment of pain
 6. Patient assessment of physical function
 7. Acute-phase reactant value

Statistical Methods:

ARMS 1-2

Longitudinal precision and camera-specific precision will be analyzed with confidence intervals for Root Mean Square Difference (RMSD) and the mean difference (i.e., the bias) between the relevant time points. Confidence intervals (95% confidence level)

will be calculated using Normal theory results ([Lin 2002](#)). As a sensitivity measure, the 80th and 90th percentiles of the distribution of the absolute differences will be computed using quantile methods.

Stability of the mean/variance relationship will be assessed with a 95% confidence interval for the difference between the CV for RA and HC subjects at each time point. If the CV for both groups at an imaging time point is less than 0.30, a 95% confidence interval based on the methods outlined in ([Forkman 2009](#)) will be provided. Because Forkman's methods are based on Normal theory, a 95% bootstrap confidence interval will also be provided for all time points.

Temporal stability of the 150 mcg dose will be assessed with a 95% Student's T interval for the difference between the TUV at 60 minutes and at 180 minutes. As a sensitivity check, a signed-rank test of the hypotheses:

$$\begin{aligned} H_0: \mu_{180} - \mu_{60} &= 0 \\ H_1: \mu_{180} - \mu_{60} &\neq 0 \end{aligned}$$

where μ_{180} represents the median TUV at 180 minutes and μ_{60} represents the median TUV at 60 minutes, will be provided.

ARM 1

Normal ranges in HC subjects will be estimated by pooling similar joints and computing the average TUV per joint per subject. The 5 and 95 percentiles will be estimated using quantile regression methods. Joints to be pooled include the following:

- Shoulders (bilateral, 2 per subject)
- Knees (bilateral, 2 per subject)
- Wrists (bilateral, 2 per subject)
- MCP (bilateral, 5 per hand, 10 per subject)
- PIP (bilateral, 5 per hand, 10 per subject)

ARM 2

The qualitative evaluations of SPECT/CT in detecting localization within synovial spaces of the bilateral hands and wrists.

ARM 3

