2 STUDY OBJECTIVES

2.1 Primary Objective(s)

- To assess the longitudinal precision of TUV_{joint} and global TUV_{global} on planar imaging in subjects with clinically diagnosed active RA on stable anti-rheumatic therapy.
- To evaluate the camera-specific precision of TUV_{joint} and TUV_{global} on planar imaging in HCs and in subjects with clinically diagnosed active RA using centralized and standardized imaging parameters.
- To assess the correlation of TUV and changes in TUV with changes in clinical assessments at multiple time points after initiation of a new anti-tumor necrosis factor alpha (TNF α) biologic disease-modifying antirheumatic drug (bDMARD) therapy.

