9.5.3 Analysis of Efficacy Variables

All efficacy analyses will be conducted on both the ITD and PP populations. The ITD population will be the primary analysis set.

9.5.3.1 Primary Endpoints Arms 1- 2

Precision endpoints will be assessed estimating the mean, standard deviation, n, minimum, median, and maximum of the signed differences, calculated as change from the initial measurement. The RMSD will be calculated and a 95% confidence interval on its value will be provided.

Stability of the mean/variance relationship will be assessed by the coefficient of variation of the differences for active RA subjects and HC subjects at 60 minutes and 180 minutes. 95% confidence intervals for the difference in CVs following the methods of ([Forkman 2009](#)) and from the bootstrap sampling distribution of the difference of the CVs will be provided based on N = 5000 bootstrap samples.

9.5.3.2 Secondary Endpoints Arms 1- 2

The normal ranges of ΔTUV_{joint} will be estimated from data collected from HC subjects (Arm 1 only) at 60 minutes and 180 minutes post-injection. The mean, standard deviation, n (number of joints), and quantile regression estimates of the 5 and 95 percentiles will be provided for shoulder, elbow, wrist, MCP, PIP, and knee.

9.5.3.3 Primary endpoint Arm 3

The Kendall rank correlation between $\Delta TUV_{global[5w]}$ with $\Delta CDAI_{12w}$ and $\Delta CDAI_{24w}$ will be computed and a 95% confidence interval for its value will be computed using Fisher's Z-transformation. Similarly, the Kendall rank correlation between $\Delta TUV_{global[5w]}$ with ΔACR_{12w} and ΔACR_{24w} (overall scores only) will be computed and a 95% confidence interval for its value will be computed using Fisher's Z-transformation.

9.5.3.4 Secondary endpoint Arm 3

The Kendall rank correlations between $\Delta TUV_{global[5w]}$ with the subscores of ΔACR_{12w} and ΔACR_{24w} (including tender joint count, swollen joint count, Patient assessment of global disease activity, Rheumatologist assessment of global disease activity, Patient assessment of pain, Patient assessment of physical function, Acute-phase reactant value) will be computed and a 95% confidence interval for its value will be computed using Fisher's Z-transformation.

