4.1.1 Primary efficacy variables

The primary efficacy variables for this study are:

- Quantitative measurement of TUV_{joint} (all arms) and TUV_{global} (Arms 2 and 3 only)
- CDAI scores at baseline, 12 (± 1) weeks and 24 (± 1) weeks (Arm 3 only)
- DAS28 scores at baseline, 12 (± 1) weeks and 24 (± 1) weeks (Arm 3 only)
- ACR Response Criteria at 12 (± 1) weeks and 24 (± 1) weeks (Arm 3 only).

The primary efficacy variables of this study in Arms 1 and 2 are:

- The camera-specific precision of TUV_{joint} and TUV_{global} in subjects with active RA and healthy controls, which is defined as the Root Mean Square Difference (RMSD) between the consecutive 15-minute planar images.
- The stability of the mean/variance relationship, which is assessed by comparing the Coefficient of Variation (CV) of TUV_{joint} and TUV_{global} in subjects with active RA and healthy controls.

An added primary variable in Arm 2 only is:

- The longitudinal (8-day) precision of TUV_{joint} and TUV_{global} in subjects with active RA, which is defined as the RMSD of the TUV between the baseline and 8 day image at the same time point.

The primary endpoints in Arm 3 are:

- The Kendall rank correlation of $\Delta TUV_{global[5w]}$ with the response to new anti-TNF α bDMARD therapy defined as $\Delta CDAI_{12w}$ and $\Delta CDAI_{24w}$ (overall scores only) in study arm 3.
- The Kendall rank correlation of $\Delta TUV_{global[5w]}$ with the response to new anti-TNF α bDMARD therapy defined as the changes from baseline in DAS28 and in each of the ACR Response Criteria components at 12 (± 1) weeks and at 24 (± 1) weeks in study arm 3.

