xxxxxxxxxxxxxxxxxx	xx	xx	xx.xxx	(xx.xxx, xx.xxx)	xx.xxx	xx.xxx	xx.xxx
xxxxxxxxxxxxxxxxxx	xx	xx	xx.xxx	(xx.xxx, xx.xxx)	xx.xxx	xx.xxx	xx.xxx

If there are no major protocol deviations, then analysis tables for the ITD and PP populations will contain identical results.

STATKING Clinical Services (DD-MMM-YYYY)

Source Program: xxxxxxx.sas

All evaluated DAS28 joints will be included in this table. Table format is repeated for the PP population.

Table 13. Assessment of Mean/Variance Relationship by Time Point
 Navidea Biopharmaceuticals - Study No. NAV3-31
 ITD Population (N=xxx)

Part 1 of 2

Global TUV or DAS28 Joint TUV	View	Reader	Arm ^a	Number of Joints					Median
				Mean	Std Dev	Minimum	Maximum		
xxxxxxxxxxxxxxxxxx	xx	xx	HC	xx	xx.xxx	xx.xxx	xx.xx	xx.xx	xx.xx
			RA-2	xx	xx.xxx	xx.xxx	xx.xx	xx.xx	xx.xx
	xx	xx	HC	xx	xx.xxx	xx.xxx	xx.xx	xx.xx	xx.xx
			RA-2	xx	xx.xxx	xx.xxx	xx.xx	xx.xx	xx.xx
	xx	xx	HC	xx	xx.xxx	xx.xxx	xx.xx	xx.xx	xx.xx
			RA-2	xx	xx.xxx	xx.xxx	xx.xx	xx.xx	xx.xx
	xx	xx	HC	xx	xx.xxx	xx.xxx	xx.xx	xx.xx	xx.xx
			RA-2	xx	xx.xxx	xx.xxx	xx.xx	xx.xx	xx.xx
	xx	xx	HC	xx	xx.xxx	xx.xxx	xx.xx	xx.xx	xx.xx
			RA-2	xx	xx.xxx	xx.xxx	xx.xx	xx.xx	xx.xx
	xx	xx	HC	xx	xx.xxx	xx.xxx	xx.xx	xx.xx	xx.xx
			RA-2	xx	xx.xxx	xx.xxx	xx.xx	xx.xx	xx.xx

^a HC = healthy control, RA-2 = rheumatoid arthritis (stable treatment regimen).

If there are no major protocol deviations, then analysis tables for the ITD and PP populations will contain identical results.

STATKING Clinical Services (DD-MMM-YYYY)

Source Program: xxxxxxx.sas

All evaluated DAS28 joints will be included in this table. Table format is repeated for the PP population, .

Table 13. Assessment of Mean/Variance Relationship by Time Point
 Navidea Biopharmaceuticals - Study No. NAV3-31
 ITD Population (N=xxx)

Part 2 of 2

Global TUV or DAS28 Joint TUV	View	Reader	Arm ^a	Coefficient of Variation	95% Confidence Limits	Bootstrap Confidence Interval
xxxxxxxxxxxxxxxxxx	xx	xx	HC	xx.xxx	(xx.xxx, xx.xxx)	(xx.xxx, xx.xxx)
			RA-2	xx.xxx	(xx.xxx, xx.xxx)	(xx.xxx, xx.xxx)
	xx	xx	HC	xx.xxx	(xx.xxx, xx.xxx)	(xx.xxx, xx.xxx)
			RA-2	xx.xxx	(xx.xxx, xx.xxx)	(xx.xxx, xx.xxx)
	xx	xx	HC	xx.xxx	(xx.xxx, xx.xxx)	(xx.xxx, xx.xxx)
			RA-2	xx.xxx	(xx.xxx, xx.xxx)	(xx.xxx, xx.xxx)

^a HC = healthy control, RA-2 = rheumatoid arthritis (stable treatment regimen).
 If there are no major protocol deviations, then analysis tables for the ITD and PP populations will contain identical results.
 STATKING Clinical Services (DD-MMM-YYYY)

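### The mean/variance primary endpoint compares between-subject CVs of TUV in RA and HC, so it mixes disease heterogeneity with scan error and can mislead about either

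*Protocol*

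**What the plan says.** Three definitions or displays of this endpoint have to be set side by side.

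- **CV of TUV itself.** The synopsis lists this primary endpoint for Arms 1-2, in which RA is the other group: "The stability of the mean/variance relationship, which is assessed by comparing the Coefficient of Variation (CV) of TUV_{joint} and TUV_{global} in HCs". Protocol 9.3 repeats it, and SAP 4.1.1 has the same definition, naming RA first and HC second: "The stability of the mean/variance relationship, which is assessed by comparing the Coefficient of Variation (CV) of TUV_{joint} and TUV_{global} in subjects with". The synopsis analysis is an interval for the difference between arms: "Stability of the mean/variance relationship will be assessed with a 95% confidence interval for the difference between the CV for RA and HC subjects". A Normal-theory interval is added where both CVs are below 0.30, and a bootstrap interval is given at all time points.
- **CV of the differences.** Protocol 9.5.3.1 says instead, for the 60- and 180-minute images: "Stability of the mean/variance relationship will be assessed by the coefficient of variation of the differences for active RA subjects and HC subjects".
- **Table shell.** SAP Appendix B, "Table 13. Assessment of Mean/Variance Relationship by Time Point", gives mean, SD and CV by joint, view, reader and arm, with limits for each arm. Nothing is labelled as a difference between scans, and there is no RA-minus-HC column. SAP Table 7, by contrast, labels its mean column as a difference.

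SAP 4.2.1 has no text for the CV analysis. No document states a null hypothesis, margin or decision rule for this endpoint. The primary objectives that Arms 1 and 2 serve concern longitudinal and camera-specific precision; the second begins "To evaluate the camera-specific precision of". Repeat-scan error has its own co-listed primary endpoint, the RMSD between consecutive scans.

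**The concern.** The CV of TUV across subjects answers whether people vary by the same proportion in RA and HC. It does not isolate whether TUV is measured with the same relative error in the two groups, which is the question that the precision objectives raise. SAP 2.5 itself expects some RA joints to lie above the healthy limit and others not, so a larger relative spread in RA is likely even if the camera performs identically in both groups. In the other direction, if people differ much more than repeat scans do, a real worsening of relative scan error in RA adds little to the total CV.

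At stake is the interpretation of a designated primary endpoint. An interval that excludes 0 could be reported as instability of the measurement when it reflects disease. An interval that covers 0 could be reported as stability when relative scan error differs. It is also the only planned RA-versus-HC comparison of variability relative to the mean.

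**Working it through.** **Inputs.** From the documents: 38 evaluable subjects in each of Arms 1 and 2, 95% intervals, and A and B scans at 60 and 180 minutes in both arms. The plan gives no sample size, power or error rate for this endpoint, so there is no figure to reproduce. Assumed, because the documents give none: between-subject CV b from 0.05 to 0.20, and measurement CV m of 0.05, or 0.10 when doubled.

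**1. What the planned CV contains.** For one scan per subject, total CV ≈ √(b² + m²). If m doubles from 0.05 (HC) to 0.10 (RA) with b equal, the log ratio of total CVs has

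SE = √[(1/(2n) + CV_HC²/n) + (1/(2n) + CV_RA²/n)], n = 38,

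and detection ≈ Φ(ln ratio/SE − 1.96), plus a negligible opposite tail.

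| b | CV in HC | CV in RA | Ratio | ln ratio / SE | Detected, formula | Detected, simulated bootstrap interval |
|---|---|---|---|---|---|---|
| 0.05 | 0.071 | 0.112 | 1.58 | 2.80 | 80% | about 80% |
| 0.10 | 0.112 | 0.141 | 1.26 | 1.43 | 30% | about 33% |
| 0.15 | 0.158 | 0.180 | 1.14 | 0.79 | 12% | about 17% |
| 0.20 | 0.206 | 0.224 | 1.08 | 0.48 | 8% | about 8% |

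Across repeat runs and interval types the four rows range over 77-81%, 28-33%, 11-17% and 7-10%.

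**2. Equal scan error, heterogeneous RA.** Set m = 0.05 in both arms and raise the joint in 30% of RA subjects (assumed). Share of simulated trials whose 95% bootstrap interval for CV(RA) − CV(HC) excludes 0:

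| b | Raised 20% | Raised 30% | Raised 50% |
|---|---|---|---|
| 0.10 | 31% | 70% | 99% |
| 0.15 | 16% | 34% | 82% |

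Scan error is identical in every cell. For example, at b = 0.10 with a 30% rise, the total CV moves from 0.112 to 0.169 through biology alone. A rise shared by all RA subjects, with SD in proportion, would leave the CV unchanged; it is heterogeneity that moves it.

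**3. The definition in protocol 9.5.3.1.** If D = A − B has true mean 0, then |SD(D)/mean(D)| = √n/|t|, where t is the one-sample t statistic. With n = 38, √38 = 6.16, and the median |t| is about 0.68, so the median absolute CV is 6.16/0.68 ≈ 9. Simulation gives a 5th to 95th percentile range of about 3 to 100. Falling below the 0.30 condition needs |t| > 6.16/0.30 = 20.5, and this did not occur in any simulated trial. Choosing this definition over the other would not repair the endpoint.

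**4. Within-subject alternative.** wCV = √(mean[(A − B)²/(2m²)]), where m is here the mean of the pair. SE of the log RA/HC ratio ≈ √(1/(2·38) + 1/(2·38)) = 0.162. For a doubling, ln 2/0.162 = 4.27 and Φ(4.27 − 1.96) = 0.99. Simulation gives 98-99%, whatever the between-subject CV. With equal error and the heterogeneity of step 2, the interval excludes equality in 6-8% of trials.

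**5. Would a stability margin work?** Take 0.67 to 1.5 as an example. The 95% interval lies inside only if |ln ratio estimate| < ln 1.5 − 1.96 × 0.162 = 0.405 − 0.318 = 0.0875. Under truly equal error the probability is 2Φ(0.0875/0.162) − 1 = 0.41.

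**The case against.** **The endpoint may never have been meant as a precision check.** It is listed as a bullet separate from RMSD, no text ties it to scan error, and interim analysis 2 shows interest in inter-subject variation for planning Phase 3. This stands in part: the between-subject CV is worth reporting. But the endpoint is primary, and the primary objectives behind Arms 1 and 2 are about precision.

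**RMSD already measures scan error in both arms.** This stands, and a reader might wrongly infer that the study ignores measurement error. It does not. RMSD is, however, in absolute units and no RA-HC comparison of it is specified, so it does not address error relative to the mean across arms.

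**Protocol 9.5.3.1 uses a within-subject quantity.** True, and the conflict must be resolved, but that quantity is unusable (step 3).

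**The sizes rest on assumptions.** This stands. TUV_joint is normalised to the same hand under SAP 2.5, so a low between-subject CV cannot be excluded. At 0.05 the planned comparison finds a doubling in about 80% of trials.

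A reader might also infer that the endpoint rejects stability, or that it undermines the 7.5% repeatability limit and the 10% response cut-off. Neither is supported. No test is planned, only intervals. The 7.5% limit is tested directly on 8-day TUV_global in Arm 2 and the 10% cut-off is applied to change in TUV_global; neither uses this result.

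**Conclusion.** The concern holds in a conditional form. As defined in the synopsis, protocol 9.3, SAP 4.1.1 and Table 13, the endpoint compares a quantity that mixes biology with scan error. Its interval can exclude 0 through RA heterogeneity alone, and it can miss a difference in relative scan error. How often depends on the ratio of between-subject to measurement CV, which the documents do not give: over the assumed range, detection of a doubling runs from about 80% down to 8%. An unconditional statement that the endpoint misses a doubling would go too far.

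Two parts do not depend on assumed CVs. The definitions in the synopsis and in protocol 9.5.3.1 conflict, and the latter fails whenever the mean A-B difference is near 0. The SAP has no analysis text or RA-HC column to settle which applies.

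**What to change.** Use one definition in the synopsis, protocol 9.3 and 9.5.3.1, SAP 4.1.1 and 4.2.1, and Table 13: the within-subject CV of TUV_joint from the consecutive A and B scans, by the wCV formula above, per joint, view, reader, arm and time point.

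- Report the RA/HC ratio of wCV with a 95% interval from a bootstrap that resamples subjects, and add this comparison to Table 13.
- Keep the present CV rows as a descriptive summary labelled as between-subject CV.
- Present the ratio and interval as estimates, and state that an interval covering 1 is not evidence of stability.
- Do not add a 0.67-1.5 margin. It would be met in only about 41% of trials with equal error, and SAP 4.2.1 records that the A/B analyses were completed in IA-3, so a margin set now would not be prespecified.
- Define separately, or remove, the HC comparison for TUV_global. SAP 4.1.1 lists that measure for Arms 2 and 3 only. SAP 2.5 builds it from joints above the normal limit, so it can be 0 and leave wCV undefined.

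Cost: text changes, one extra block in Table 13 and a short program. The A and B scans are already part of the plan in both arms. Intervals for single joints will be wide: with an SE of 0.162 on the log scale, the 95% limits are about 1.37-fold either side of the estimate (exp(0.318)).

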ACR20/50/70	American College of Rheumatology response criteria
ACR/EULAR	American College of Rheumatology/European League Against Rheumatism
AE	Adverse event
ALT	Alanine aminotransferase
AST	Aspartate aminotransferase
AUC	Area under the curve
bDMARD	Biological disease-modifying antirheumatic drug
BMI	Body mass index
CD206	Mannose-binding receptor (Ca2+-binding lectin)
CDAI	Clinical disease activity index
CFB	Change from baseline
CRF	Case report form
CRO	Contract research organization
CRP	C-reactive protein
CV	Coefficient of variation
DAS28	Disease activity score -28 for RA describing the severity of RA using clinical and laboratory data.
DMARD	Disease-modifying antirheumatic drug
DTPA	Diethylenetriaminepentaacetic Acid

ECG	Electrocardiogram
eCRF	Electronic case report form
ESR	Erythrocyte sedimentation rate
GCP	Good Clinical Practice
HAQ-DI [®]	Health Assessment Questionnaire - Disability Index
HC	Healthy control
ICF	Informed consent form
ICH	International Conference on Harmonization
IHC	Immunohistochemistry
ITD	Intent to diagnose
IND	Investigational New Drug
IRB	Institutional Review Board
IV	Intravenous
MCP	Metacarpophalangeal joint
NSAID	Non-steroidal anti-inflammatory drug
p.i.	Post injection
PIP	Proximal interphalangeal
PK	Pharmacokinetics
PP	Per Protocol
QT	Interval from the Q wave to the end of the T wave
QTc	Corrected QT interval
RA	Rheumatoid arthritis
RF	Rheumatoid factor
RMSD	Root mean square difference
ROC	Receiver operating characteristic
ROI	Region of interest
RR	Reference region
RSNA	Radiological Society of North America
SAP	Statistical analysis plan

SJC	Swollen joint count
SC	Sulfur colloid
SOC	System organ class
SPECT	Single-photon emission computerized tomography
SPECT/CT	Combined single-photon emission computerized tomography and computed tomography
TJC	Tender joint count
TMF	Trial master file
TNF α	Tumor necrosis factor alpha
TUV	Tilmanocept uptake value
TUV _{global}	Global tilmanocept uptake value
TUV _{joint}	Joint-specific tilmanocept uptake value
UC	Uncertainty coefficient
ULN	Upper limit of normal
VAS	Visual analog scale
WB	Whole body
WPI	Widespread pain index

1 INTRODUCTION

1.1 Background

Worldwide, approximately 1 in 200 adults suffer from RA. In the US, 1.3 million adults are living with RA. Each year, about 130,000 Americans are newly diagnosed with RA. Persons with inadequately controlled RA have significantly shorter life expectancies and frequently become disabled, leading to reduced quality of life and severe adverse economic consequences ([Lassere 2013](#), [Michelsen 2018](#), [Uhlig 2014](#), [Verstappen 2015](#)).

It has been realized for many years that RA patients who are placed on DMARDs soon after they develop arthritis symptoms respond much more favorably to these therapies than do patients whose initiation of DMARD therapy is delayed ([Demoruelle 2012](#)). Many more of these early RA patients placed on therapy achieve disease remission than is observed in RA patients who do not initiate DMARD therapy until after they have been symptomatic for RA for 6 or more months. Furthermore, those early RA patients placed on timely therapy who do not achieve remission experience less severe disease ([Anderson 2000](#), [Nell 2004](#), [van der Linden 2010](#)). Indeed, the early diagnosis of RA affords a “window of opportunity” for the greatest probability of effective RA therapy and the possibility of disease remission ([Cush 2007](#)). This window closes 3 to 6 months after patients become symptomatic with RA. The problem is that only a portion of patients first presenting with arthritis have RA and differentiating those patients who have RA from those who do not is challenging, leading frequently to delays in accurately identifying those patients with RA.

The realization that early diagnosis of RA is critical for delivering the most effective RA treatment led to a collaboration between the American College of Rheumatology and the European League Against Rheumatism (ACR/EULAR) that resulted in 2010 in the publication of new criteria for diagnosing RA ([Aletaha 2010](#)). The intent of the ACR/EULAR 2010 criteria was to improve the diagnosis of early RA. This intent was only partially realized. There have been numerous publications reporting the results of studies evaluating the diagnostic accuracy of the ACR/EULAR 2010 criteria for identifying early RA patients. In a meta-analysis of this literature ([Sakellariou 2013](#)), it was shown that the ACR/EULAR 2010 criteria has a 73% sensitivity and a 74% specificity for correctly identifying early RA. If the ACR/EULAR 2010 criteria are used to decide who should receive DMARD therapy, this meta-analysis indicates that over a quarter of true early RA patients would not be provided with appropriate DMARD therapy during the critical window of opportunity for an optimal response. Furthermore, a significant portion of arthritis patients who do not have RA would be prescribed DMARD therapies for which they would not receive benefit and would be exposed to possible adverse side effects of the drugs. Clearly there remains an unmet need for a more accurate means to identify early RA patients, to improve aggregate outcomes for early RA patients, and to reduce adverse drug effects and healthcare costs associated with unproductive delivery of RA therapies to individuals who do not have RA.

Basic research on the pathobiology of RA has revealed that the inflammation observed in RA is the consequence of a self-perpetuating pathological alteration in the expression and downstream signaling of a network of cytokines ([Meyer 2010](#), [Olszewski 2001](#)). Frequently,

at the center of this cytokine network is the overexpression of tumor necrosis factor alpha (TNF α) (Choy 2001, Keffer 1991, Leizer 1990, Westra 2004). Recognition of the importance of disturbances in cytokine expression and especially that of TNF α formed the underlying rationale for the development of many antibody based biologic therapies intended to block signaling by TNF α or one of the other various inflammatory cytokines involved in RA pathology (Chen 2006, Kalden 2002, Scott 2010, Vivar 2014). Many of these cytokine-directed RA biologic therapies have been granted regulatory approval and are currently commercially available. While many RA patients have benefited from recent advances in RA therapies, problems and deficiencies remain. Among these problems and deficiencies are:

- A significant portion of RA patients do not respond to RA therapies or respond insufficiently to RA therapies to achieve therapeutic goals (Furst 2011, Salliot 2011),
- All current RA therapies are associated with adverse effects, which can be common and/or severe (Tran 2013),
- Many current RA therapies, especially the biologic therapies, are exceedingly expensive, placing an imposing burden on healthcare costs (Hresko 2018) and affordability (Heidari 2018), and
- Nearly all RA therapies lack an adequate defined diagnostic element that can facilitate choosing an individual patient's therapeutic regimen that provides the highest probability of an effective treatment response.

Quantitative assessment of CD206 positivity of inflamed synovia in RA patients is expected to remedy, at least partially, all 4 of these problems and deficiencies. Tc 99m tilmanocept is a synthetic radiopharmaceutical imaging agent that was purposefully designed to be a high affinity ligand for CD206. CD206 is highly upregulated on phenotypically activated macrophages that contribute mechanistically to the underlying pathobiology of RA. It has long been recognized that activated macrophages contribute significantly to RA pathology (Firestein 1990, Ishikawa 1976, Kinne 2007). Macrophages are common in inflamed synovial tissues when patients are first diagnosed with RA (Smolen 2018) and frequently become more numerous as the disease progresses. Activated macrophages produce most of the TNF α that, in a significant proportion of cases, drives and perpetuates the inflammatory cycle in RA (Choy 2001). In the synovial sublining of a joint affected by RA, activated macrophages are frequently the dominant cell type (Cutolo 1993, Kennedy 2011, Kraan 2002). Activated macrophages significantly contribute to the destruction of bone and cartilage through their secretion of proteases (Bresnihan 1999, Ma 2005). Furthermore, the densities of synovial membrane macrophages measured before treatment, and especially the densities of sublining macrophages, have been reported to predict future joint damage (Mulherin 1996, Orr 2017a, Vieira-Sousa 2011, Yanni 1994). Not surprisingly, activated synovial macrophage numbers—but not the numbers of other immune cell types—correlate with radiographically determined joint destruction in RA (Mulherin 1996, Yanni 1994). Thus, CD206 positivity of inflamed synovia in RA patients is expected to provide clinically significant prognostic information for RA patients. Another important finding is that activated macrophage numbers are reduced by effective RA therapy (Vieira-Sousa 2011), but do not significantly change over the course of at least months if a patient was given ineffective RA therapy (Baeten 2006). Also, importantly, reductions in activated synovial macrophages associated with effective RA therapy typically

occur *before treatment mediated changes* in the severity of clinical symptoms can be observed (Filkova 2016). Thus, a change in activated synovial macrophage numbers is now recognized as a biomarker that provides an objective and early measure of responses to RA therapies (Bresnihan 2009, Smith 2001). In fact, a change in activated synovial macrophage numbers is considered a more accurate measure of treatment response than clinical assessments, which are highly subjective in nature and prone to observer error (Bresnihan 2009, van de Sande 2012, Wijbrandts 2007). Therefore, there is a possibility that future clinical studies may show that quantitative assessment of CD206 positivity of inflamed synovia in RA patients could be used to monitor the efficacy of RA therapies, providing physicians and patients with earlier and more objective criteria to abandon ineffective therapies and adopt alternative therapies that may be more effective.

In recent years, synovial biopsy-enabled studies have greatly increased our understanding of the pathological processes occurring within the inflamed joints of RA patients (Orr 2017a). An important finding of these studies has been that the inflammatory cell compositions of RA inflamed joints can vary between patients (Townsend 2014, van de Sande 2016). The biopsy specimens obtained from different RA patients can have different numbers and densities of macrophages and monocytes, lymphocytes and lymphocyte containing structures, and fibroblast-like synoviocytes (Orr 2017b). These differences in cellular composition suggest that RA inflammation can be divided into 3 pathotypes, referred to as diffuse myeloid, lympho-myeloid, and fibroid respectively (Astorri 2015, Dennis 2014). Myeloid pathotype variants have the highest density of macrophages, whereas the fibroid pathotype is largely devoid of both macrophages and lymphoid cells. These pathotypes are not fully discreet with some overlap occurring. However, they provide a strong basis for temporal or cytological compartmentalization in RA disease natural history.

Current studies utilizing IHC analyses of synovial biopsies are insufficient to determine the distribution of the various pathotypes in RA patients but suggest that the diffuse myeloid and lympho-myeloid pathotypes are about equally frequent in RA patients with the fibroid pathotype being less common. There is growing evidence that patients with different RA pathotypes respond differently to various therapies, holding out the possibility that determining the RA pathotype of an individual patient's RA can direct choice of the most effective therapy for that patient (i.e., personalized RA therapy) (Dennis 2014). This is an area of ongoing active investigation in RA therapy research (Donlin 2018, Mandelin 2018, Pitzalis 2013). However, already there is significant evidence indicating that patients with a myeloid-driven RA pathotype and/or with high densities of macrophages in their inflamed synovium respond best to anti-TNF α biologic therapy (Dennis 2014, Wijbrandts 2008), whereas patients with a fibroid pathotype do not respond significantly to anti-TNF α therapy. Although these results need to be confirmed and elaborated upon in further studies, they suggest that determination of the density of activated macrophages in the inflamed synovial membranes of patients with RA could facilitate identification of those RA patients who would most benefit from anti-TNF α therapy and/or those who would not receive benefit. Additional work in this field seeks to determine if similar associations between the efficacies of other treatments and synovial pathotypes can identify those treatments that are most effective in patients with lympho-myeloid and/or fibroid RA pathotypes. Such results, if attained, would provide a great benefit to RA patients by enabling personalized delivery of an optimal treatments to all RA patients.

Previously generated results from clinical imaging studies conducted by Navidea and extensive peer reviewed scientific literature strongly indicate that Tc 99m tilmanocept can enable non-invasive imaging of aggregates of CD206 expressing cells associated with various pathologies using planar scintigraphy. While it has been suggested that synovial biopsy and IHC evaluations might be translatable to common rheumatological clinical practice, there are 5 reasons why quantitative assessment of CD206 positivity enabled by Tc 99m tilmanocept imaging may be preferred to synovial biopsies for evaluations of RA patients.

First, biopsy procedures usually sample a single joint. If variation exists between the pathotypes of different joints in the same patient, biopsy studies cannot detect or quantify this variation. Current RA therapies and new therapies in development are, by their designed targets, likely to be more effective against specific RA pathotypes. If pathotype variation occurs within individual RA patients, this could severely limit the ability of pathotype determination by biopsy to accurately predict treatment response. A key advantage of Tc 99m tilmanocept imaging over synovial biopsies is that Tc 99m tilmanocept imaging can provide a global quantitative assessment of all joints, providing Tc 99m tilmanocept imaging with the possibility of detecting pathotype variation without biopsies. Navidea's proposed studies will directly assess RA inflammatory variation within individual patients and provide evidence relevant to determining the extent to which pathotype variation exists within individual RA patients and the ability of Tc 99m tilmanocept imaging to detect this variation.

The second reason why Tc 99m tilmanocept imaging may be preferred to synovial biopsies for evaluations of RA patients is that synovial biopsies are only performed on patients with inflamed synovia that have expanded in volume beyond a certain grade, thereby enabling extraction of sufficient tissue to assess histologically. This could be a problem when evaluating patients in the early phase of symptomatic RA disease when high densities of activated macrophages have begun to aggregate into the inflamed synovial membrane but the synovial membrane may not yet have expanded (i.e. thickened) sufficiently to permit biopsy sampling. As discussed below, there is an urgent need to more accurately identify RA patients as early in the disease process as possible and place them on DMARD therapy immediately to provide these patients with their best possible therapy responses.

The third reason why Tc 99m tilmanocept imaging may be preferred to synovial biopsies for evaluations of RA patients is that, although synovial biopsy procedures typically extract 6-14 samples of tissue from each biopsied joint, in about 5% to 10% of cases, they do not provide tissue of sufficient quantity or quality to enable adequate histological evaluations of the inflamed synovial tissue (Kraan 2002, Pitzalis 2013). It is expected that Tc 99m tilmanocept imaging would not fail to quantitatively assess the aggregation of macrophages in RA inflamed joints at this frequency.

The fourth reason is that although more than 1 biopsy procedure can be performed on an individual joint, there are likely to be limitations on the number of times or how often a single joint can be biopsied. Furthermore, while not discussed in the literature, repeated biopsies may alter the inflammatory microenvironment in an inflamed synovial membrane and/or induce its own inflammation or wound healing response to trauma. In any event, Tc 99m tilmanocept imaging, being non-invasive and non-traumatic, is likely to be more amenable to repeat

examination and would not affect synovial inflammation through repeated biopsy related trauma. These issues may be most significant when considering evaluations of the small joints of the hands where there is a limited quantity of inflammatory tissue.

The fifth and final reason why Tc 99m tilmanocept imaging will be preferred to synovial biopsies is that performing biopsies is challenging and requires extensive training ([Mandelin 2018](#)). Synovial biopsies have only been performed in research settings and until very recently, only in Europe where adequately trained and experienced investigators reside. Training and qualifying all physicians in the US who care for RA patients to perform synovial biopsies would be a significant barrier to adoption.

Indeed, Tc 99m tilmanocept quantitative imaging reliably assesses all joints, is not dependent on synovial swelling, is non-invasive and non-traumatic, and does not require extensive practitioner training. Thus, for all these reasons, Tc 99m tilmanocept imaging is expected to provide clinically predictive information about the inflammatory status of inflamed joints in RA patients that is not obtainable from synovial biopsies or will be preferred over invasive and potentially risky synovial biopsies as a means to evaluate RA patients.

